3.3.1.2 Patient Reported Demographic and Sociodemographic Variables

- **Age**—Age will be calculated from the 1-item survey question asking patients to provide their year of birth; claims data may supplement patient-report for subjects who do not respond to this item.
- **Age groups**—Subjects will be assigned to an age group based on the distribution of the age measure, for example: 65-69, 70-74, and 75+.
- **Gender**—Gender will be captured from a single-item survey question; claims data may supplement patient report for subjects who do not respond to this item.
- **Race**—Whether the respondent considers themselves to be American Indian or Alaskan Native, Asian, Black or African American, Native Hawaiian or Pacific Islander, White, and/or Other race.
- **Ethnicity**—Whether the respondent identifies as Hispanic/Latino.

- **Population density**—Defined by a single question asking patients to identify whether the community they live in is urban, suburban, or rural.
- **Marital status**—Defined by a single question asking patients to identify whether they are single/never married, living with partner, married, separated, divorced, or widowed.
- **Educational attainment**—The highest level of education the patient has completed will be measured as some high school, high school or equivalent (e.g., GED), some college but no degree, two-year college, four-year college, or graduate school.
- **Income**—Annual income for the last completed calendar year will be collected as less than \$30,000, \$30,000-\$49,999, \$50,000-\$74,999, \$75,000-\$99,999, \$100,000 or greater, or I choose not to answer.

3.3.1.3 Patient-reported COPD Symptom Burden

- **Dyspnea**—Breathlessness will be assessed using the Modified Medical Research Council Dyspnea scale (mMRC), a single item (0-4 scale) to assess patients' current level of dyspnea.^{iv,v} The mMRC is comprised of five statements that describe almost the entire range of respiratory disability from none (Grade 0) to almost complete incapacity (Grade 4). The score (Grade) is the number that best fits the patient's level of activity.
- **Burden of illness**—Condition-related well-being will be assessed using the COPD Assessment Test (CAT), an eight-item validated questionnaire developed by GSK to determine the impact of COPD on the patient's well-being and daily life.^{vi, vii} The items of CAT measure the most salient symptoms of COPD, including cough, chest tightness, breathlessness, and activity limitation attributed to COPD symptoms. Each of the items of CAT is scaled on a 0-5 point scale with higher values indicative of worse health status. The item response values of CAT are summed to produce a single score that ranges from 0 (best health status) to 40 (worst health status). The reference period is current.

3.3.2 Claims-based Measures

General descriptions of claims data based study variables are provided below. All variable definitions, including diagnosis codes, procedures codes, medication lists, and algorithms will be provided in detail in the SAP. Patients' clinical and treatment characteristics will be measured in the baseline period, defined as the 12-month period prior to survey sample identification.

3.3.2.1 Claims-based Clinical and Treatment Characteristics

- **Baseline Quan-Charlson comorbidity score**—A comorbidity score will be calculated based on the presence of diagnosis codes on medical claims in the baseline period.^{viii,ix} The Quan-Charlson comorbidity score will also be categorized into the following groups: zero, one to two, three to four, and five or more. The mean comorbidity score will be presented.
- **Baseline comorbid conditions**—General comorbid conditions will be defined using the Clinical Classifications Software managed by the Agency for Healthcare Research and Quality (AHRQ)^x. This measure generates indicator variables for specific disease conditions based on ICD-10-CM diagnoses codes. The top 20 comorbid conditions will be presented.
- **COPD-related comorbid conditions**—In addition, whether or not patients have evidence of specific COPD-related comorbidities will be assessed for approximately 10 COPD-related conditions. Conditions of interest may include, for example, upper and lower respiratory infections, type 2 diabetes mellitus (T2DM), pulmonary hypertension, and obstructive sleep apnea. A binary indicator will be created for each condition to identify whether or not the patient has claims-based evidence of that condition. Counts and percents will be presented. Codes for conditions of interest will be specified in the SAP.

- **Baseline medications**—A count of unique medications filled in the baseline period will be calculated.
- **Baseline medication dispensings**—A count of unique dispensings for all medications filled in the baseline period will be calculated.

3.3.2.2 Claims-based Health Care Resource Utilization and Costs

- **All-cause baseline health care resource utilization**—Binary indicators and counts of ambulatory (physician office and hospital outpatient) visits, ED visits, and inpatient stays will be calculated in the 12-month baseline period.
- **All-cause baseline health care costs**—Consumer Price Index-adjusted costs will be assessed for the 12-month baseline period. Costs will be calculated as total costs, pharmacy costs, and medical costs; medical costs include ambulatory (physician office and hospital outpatient) costs, emergency costs, inpatient costs, and other costs.
- **COPD-related baseline health care resource utilization**—Binary indicators and counts of ambulatory (physician office and hospital outpatient) visits, ED visits, and inpatient stays will be calculated in the 12-month baseline period. Utilization will be defined as COPD-related when a diagnosis code for COPD (Figure 2) is in the primary position.
- **COPD-related baseline health care costs**—Consumer Price Index-adjusted costs will be assessed for the 12-month baseline period. Costs will be calculated as total costs, pharmacy costs, and medical costs; medical costs include ambulatory (physician office and hospital outpatient) costs, emergency costs, inpatient costs, and other costs. Costs will be defined as COPD-related if the claim has a diagnosis code for COPD (Figure 2) in the primary position or is for a medication used to treat COPD. Codes for COPD treatment will be provided in the SAP (and will include those in Figure 3).

Payments from Medicare are estimated based on coordination of benefits information obtained by the health plan in its usual course of business. This study will incorporate the amounts estimated to be paid by other payers (i.e., Medicare) for a total paid or allowable amount^{xi}.

- **COPD exacerbations**—Whether the patient has evidence of a COPD exacerbation during the 12-month baseline period will be captured. The count of exacerbations will be presented. GSK's harmonized exacerbation definition will be used; the definition will be included in the SAP.
- **COPD exacerbation-related baseline health care costs**—CPI-adjusted costs will be assessed for the 12-month baseline period. Total costs (pharmacy + medical) will be reported. Costs will be attributed to an exacerbation per GSK's harmonized exacerbation definition.

3.3.2.3 Claims-based Patient Demographic Measures

- **Age**—Age will be defined as of the first date of the survey fielding period.
- **Age groups**—Subjects will be assigned to an age group as described in Section 3.3.1.2
- **Gender**—Gender will be captured from enrollment data; subjects with undefined gender will be removed from the study sample.
- **Geographic region**—The U.S. region in which the study subject is enrolled in a health plan will be determined and reported and states will be categorized into four geographic regions in accordance with the U.S. Census Bureau's region designations; the four health plan regions are presented in Figure 5 below.

Figure 5 – Health Plan Regions

Region	Division	State
Northeast	New England	CT, MA, ME, NH, RI, VT
	Mid Atlantic	NJ, NY, PA
Midwest	East North Central	IL, IN, MI, OH, WI
	West North Central	IA, KS, MN, MO, ND, NE, SD
South	South Atlantic	DC, DE, FL, GA, MD, NC, SC, VA, WV
	East South Central	AL, KY, MS, TN
West	West South Central	AR, LA, OK, TX
	Mountain	AZ, CO, ID, MT, NM, NV, UT, WY
	Pacific	AK, CA, HI, OR, WA

3.3.3 Medicare Advantage Data Source

Medical and pharmacy claims data are available for approximately 4.2 million enrollees since 2006 that are enrolled in Medicare Part C (commonly referred to as the Medicare Advantage program) through an offering associated with Optum. Prior to 2006, data were available for approximately 500,000 of these enrollees. Medicare Advantage enrollees choose to receive all of their health care services through a provider organization in lieu of Medicare Part A/B coverage (commonly referred to as Medicare Fee for Service).

Claims for pharmacy services are typically submitted electronically by the pharmacy at the time prescriptions are filled. The claims history is a profile of all outpatient prescription pharmacy services provided and covered by the health plan. Pharmacy claims data include drug name, dosage form, drug strength, fill date, days of supply, financial information, and de-identified patient and prescriber codes, allowing for longitudinal tracking of medication refill patterns and changes in medications.

Medical claims or encounter data are collected from all available health care sites (inpatient hospital, outpatient hospital, ED, physician's office, surgery center, etc.) for virtually all types of provided services, including specialty, preventive and office-based treatments. Medical claims and coding conform to insurance industry standards. Claims for ambulatory services submitted by individual providers, e.g., physicians, use the Health Care Financing Administration (HCFA)-1500 or Centers for Medicare and Medicaid Services (CMS)-1500 formats. Claims for facility services submitted by institutions, e.g., hospitals, use the Uniform Billing (UB)-82, UB-92, UB-04, or CMS-1450 formats. Medical claims include: multiple diagnosis codes recorded with the International Classification of Diseases, Tenth Revision, Clinical Modification (ICD-10-CM) diagnosis codes; procedures recorded with ICD-10-CM procedure codes, Current Procedural Terminology (CPT), or Healthcare Common Procedure Coding System (HCPCS) codes; site of service codes; provider specialty codes; revenue codes (for facilities); paid amounts; and other information. Facility claims do not generally include medications dispensed in hospital.

Pharmacy claims are typically added to the research database within six weeks of dispensing. Approximately six months following the delivery of services are required for complete medical data for MA enrollees.

3.4 Endpoints

Patient-reported outcomes, which include all primary endpoints, will be measured using the cross-sectional survey at the time of survey administration. Claims-based characteristics, including economic endpoints, will be measured in the baseline period, which is the 12-month period prior to survey sample identification.

3.4.1 Primary Endpoint

- **Patient-reported symptom burden.** Scores will be presented from validated instruments measuring dyspnea (mMRC) and condition-related burden of illness (CAT). Mean total, summary, and/or domain scores and standard deviations will be presented for each scale/item (as described in Section 3.3.1.3). The proportion of patients with high and low symptom burden on both PRO measures will be calculated. Results will be presented for the overall study sample and by treatment cohort (FLUT/SAL or UMEC/VI).
- **Proportion of patients reporting COPD symptoms while treated with FLUT/SAL or UMEC/VI.** The proportion of patients who report COPD symptoms will be computed for survey respondents. Two calculations will be presented: the number of COPD patients who report COPD symptoms as measured by a CAT total score ≥ 10 , divided by the total number of respondents with a CAT total score; and the number of COPD patients with an mMRC score of 2-4, divided by the total number of respondents with an mMRC score. Results will be presented for the overall study sample and by treatment cohort.
- The mMRC and CAT instruments are included to correspond with current GOLD guidelines.

3.4.2 Secondary Endpoint(s)

- **Baseline health care resource utilization and costs.** All-cause and COPD-related health care costs will be presented for the 12-month baseline period. Mean, median, and standard deviations will be presented for total costs and utilization and for each category of costs (i.e., pharmacy + medical, and the subcategories of medical costs as described in Section 3.3.2.2). Costs and counts will be presented overall and for the subset of patients utilizing the selected type of service. The proportion of patients receiving services for each type of service and the proportion of patients with non-zero costs for each type of cost will be calculated. Results will be presented for the overall study sample and may be stratified by relevant subgroups for analysis (e.g., by low versus symptom burden as measured by patient mMRC and CAT scores).
- **Patient clinical characteristics.** The proportion of patients with evidence of selected clinical characteristics will be presented. The top 20 claims-based comorbidities and up to 10 COPD-related comorbidities will be identified. The percent of patients with each condition will be identified. Mean and standard deviation will be calculated for the Quan-Charlson comorbidity score. Results will be presented for the overall study sample and may be stratified by relevant subgroups for analysis (e.g., by low versus high symptom burden as measured by patient mMRC and CAT scores).
- **Patient GOLD classification.** The proportion of patients in each GOLD category of symptom burden and exacerbation will be presented. The calculation will use count of COPD exacerbations during the baseline combined with CAT total score and mMRC score to create mutually exclusive counts for each category (A, B, C, D) (Section 10, Appendix 3).

3.5 Sample Size / Power Calculations

The sample size required for the study is based on several requirements. First, the study's primary outcome measures will be proportions (e.g., the proportion of patients experiencing symptoms who report low versus high symptom severity as measured by the mMRC and CAT total score). The estimated sample size is determined by the value and desired precision of the measured proportions.

Figure 6 displays the sample sizes required for various proportions, assuming a 95% confidence interval and a precision of ± 0.05 . Because the actual population proportions (e.g., the proportion of patients in each treatment cohort with mMRC scores ≥ 2 and the proportion of patients in each treatment cohort with CAT total scores ≥ 10) are unknown, the largest sample size indicated with that precision was selected. This largest value is for a proportion of 0.5 and assures a 95% confidence interval of ± 0.05 or

better for all proportions observed. Thus, a sample size of 385 completed patient surveys per treatment cohort was selected.

Figure 6 – Sample Sizes Required for Various Proportions

95% Confidence Interval	Proportion								
	0.9	0.8	0.7	0.6	0.5	0.4	0.3	0.2	0.1
±0.05	139	246	323	369	385	369	323	246	139

Since the proportion of patients experiencing symptoms will be determined from the survey and a variety of exclusion criteria can be applied only after data collection, a sampling frame of 2,700 patients is needed for an estimated evaluable sample size of 385 patients per treatment cohort. The sampling frame will be comprised of equal proportions per medication cohort (n=1,350 per cohort); however, proportional response rate by treatment cohort cannot be guaranteed. Based on the feasibility counts, Optum estimates that two waves of sample identification and survey data collection will be required to meet the target sample size. Sample identification for wave 2 will occur as soon as sufficient sample is available, which is estimated to be the month following wave 1 sample identification. The availability of the second wave will be assessed during protocol development.

Figure 7 – Estimated Final Evaluable Sample Size

Sampling frame per treatment cohort	n=1,350
Estimated response rate (30-35%)	405-470
Exclusion criteria applied following claims lag (2-5% ineligible)	8-24
Estimated final evaluable sample size per treatment cohort	385-446
Estimated total final evaluable sample size	770-892

A recent feasibility assessed counts of MA patients with ≥ 2 COPD diagnoses initiating UMEC/VI or FLUT/SAL and found sufficient counts to develop a sampling frame. Based on these counts, there will likely not be enough sample who meet all eligibility criteria to complete data collection in one wave. Therefore, it is estimated that two waves of sample identification will be required to meet the target sample size based on these estimates of counts of eligible patients and response rate.

Table 1 – Feasibility Counts

Sample Attrition	Medicare Advantage n (%)
Patients with evidence of >=2 codes for treatment with Anoro Ellipta OR >=2 codes for treatment with Advair Diskus 250mg from 01Mar2017-31Aug2017	28,157
Patients with >=2 COPD diagnosis from 01Sep2016-31Aug2017	4,391 (15.6%)
Patients aged >=65 on 01Sep2016	3,224 (11.5%)
Patients with 12 months continuous enrollment 01Sep2016-31Aug2017	2,070 (7.4%)
Patients with claims for only Anoro Ellipta from 01Mar2017- 31Aug2017 and no evidence of Anoro Ellipta or Advair Diskus use from 01Sep2016- 28Feb2017	977 (47.2%)
Patients with claims for only Advair Diskus 250 mg from 01Mar2017- 31Aug2017 and not evidence of Advair Diskus or Anoro Ellipta use from 01Sep2016-28Feb2017	1,064 (51.4%)
Patients with >= 1 claim for Anoro Ellipta AND Advair Diskus 250mg from 01Mar2017-31Aug2017*	29 (1.4%)

*Patients with claims for both treatments in the 6 months prior to sample identification will be excluded.

3.6 Hypotheses

The primary objective is to assess patient-reported COPD symptom burden among patients treated with UMEC/VI as compared to FLUT/SAL. The hypothesis for the primary objective is:

Null hypothesis:

- 1A) Patient-reported symptom severity as measured by CAT total score will not differ for UMEC/VI patients as compared to FLUT/SAL patients.
- 1B) Patient-reported symptom severity as measured by mMRC score will not differ for UMEC/VI patients as compared to FLUT/SAL patients.

Alternative hypothesis:

- 1A) Patient-reported symptom severity as measured by CAT total score will differ for UMEC/VI patients as compared to FLUT/SAL patients.
- 1B) Patient-reported symptom severity as measured by mMRC score will differ for UMEC/VI patients as compared to FLUT/SAL patients.

Hypotheses are presented for the primary objective since the sample size / power calculations are based on assessment of the primary objective.

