
	
count of COPD exacerbations combined with CAT total score and mMRC score. GOLD categories are mutually exclusive. Results will be presented overall and by treatment cohort (FLUT/SAL or UMEC/VI).
 
Multivariable modeling of the primary objective will be conducted following review of descriptive and IPTW results. Each model will examine the relationship between symptom burden and treatment with FLUT/SAL or UMEC/VI. The dependent variable for the models will be CAT total score and mMRC score, respectively; covariates for the models will be based on clinical and analytic significance.

Sample Size and Power
	
The study sample is estimated to include 385 patients per cohort with evidence of COPD diagnosis and single-inhaler dual therapy treatment with FLUT/SAL or UMEC/VI. A sample size of n=385 per cohort is required to assess statistical significance with a 95% confidence interval at ± 0.05 with 80% power. A sampling frame of 2,700 patients is estimated to be used to reach the target evaluable sample size, n=770 patients (385/cohort). Based on patient counts and response rate estimates, it is anticipated that two waves of data collection will be needed to meet the target sample size.
 
This estimated study sample size is sufficient to detect proportional differences in PRO outcomes between two cohorts of patients (i.e., patients treated with FLUT/SAL or UMEC/VI who have severe symptoms as measured by a CAT total score ≥ 10 or an mMRC score ≥ 2); other stratifications tied to primary and secondary endpoints may be considered for statistically powered analyses as sample size allows.

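### Section 3.6 tests one primary objective through two nulls (CAT, mMRC) with no rule linking them, and section 4.5 leaves the outcomes and their form open until results are reviewed

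*Combined protocol and SAP*

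**What the plan says.** Section 3.6 uses the singular, "The hypothesis for the primary objective is", and then gives two nulls. One concerns CAT total score. The other reads "1B) Patient-reported symptom severity as measured by mMRC score will not differ for UMEC/VI patients as compared to FLUT/SAL patients". The alternatives are two-sided: "Patient-reported symptom severity as measured by CAT total score will differ for UMEC/VI patients as compared to FLUT/SAL patients". No and/or rule, test order or test-level alpha is given there or elsewhere in the protocol.

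Section 3.4.1 also lists two proportions as primary endpoints, with numerators "the number of COPD patients who report COPD symptoms as measured by a CAT total score ≥ 10" and "the number of COPD patients with an mMRC score of 2-4". On their use it says "Results will be presented for the overall study sample and by treatment cohort". Neither proportion has a null in 3.6.

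Section 3.5 says that "the study's primary outcome measures will be proportions" and derives 385 per cohort from them. The synopsis adds "This estimated study sample size is sufficient to detect proportional differences in PRO outcomes between two cohorts of patients" and mentions 80% power without naming a difference. Section 4.3 also ties the primary objective to the low-severity and high-severity proportions.

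Section 4.5 names CAT total score and mMRC score as the dependent variables of two models. It also says that the final model outcomes are chosen once descriptive results, including PRO scores and weighted results, have been reviewed. Each outcome may be continuous or dichotomous, depending on its distribution. The CAT cut is ≥10 in the synopsis, 3.4.1 and 3.5, but >10 in 4.3 and 4.5.

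**The concern.** A reader of the final report will want one answer: does symptom burden differ between the cohorts? The plan offers a CAT score comparison, an mMRC score comparison and two proportions, and does not say which of them decides. If whichever comparison reaches significance may carry the conclusion, the error rate for that conclusion exceeds the rate for any single test. Section 4.5 adds a freedom that cannot be quantified in advance, because the outcomes and their form can be settled by people who have already seen the results.

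The synopsis gives the purpose as supporting GOLD category B recommendations, and the plan states formal nulls and a power figure. A confirmatory reading of a positive result is therefore foreseeable.

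**Working it through.** **Inputs.** From the protocol: two score-level nulls, two-sided (3.6); two dichotomised primary endpoints (3.4.1); 385 per cohort from a proportion of 0.5 and a 95% interval of ±0.05 (3.5). Assumed, because the protocol does not give them: 5% per test, suggested only by the 95% interval wording; the CAT–mMRC correlation; the share of patients above each cut.

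**1. The plan's own figure.** n = z²p(1−p)/d² = 1.96² × 0.25 / 0.05² = 384.15, so 385. The same formula reproduces all nine cells of Figure 6 (139, 246, 323, 369, 385 and the mirror values). It gives the precision of one proportion in one cohort; no between-cohort difference enters it.

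As a two-cohort comparison, power = Φ{[d√n − z√(2p̄(1−p̄))] / √(p₁(1−p₁) + p₂(1−p₂))}. At n = 385 and two-sided 5%:
- 0.50 against 0.60: (1.962 − 1.379)/0.700 = 0.833, power 79.8%.
- 0.50 against 0.55: (0.981 − 1.384)/0.705 = −0.572, power 28%.

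The 80% in the synopsis therefore corresponds to a difference of about 10 points when one proportion is 0.50, and the plan does not state that difference.

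**2. Two nulls, either one sufficient.** Error = 1 − P(|Z₁| ≤ 1.96 and |Z₂| ≤ 1.96), with Z₁, Z₂ bivariate normal:

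| Correlation | Chance of at least one false rejection |
|---|---|
| 0 | 1 − 0.95² = 9.75% |
| 0.5 | 9.1% |
| 0.7 | 8.4% |
| 0.9 | 7.0% |

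**3. All four comparisons formally tested, any one sufficient.** Independence would give 1 − 0.95⁴ = 18.5%, which is too high because each score is strongly correlated with its own dichotomy. Correlated CAT and mMRC values were simulated and cut at CAT ≥10 and mMRC ≥2. Four null test statistics were then drawn with the resulting correlations (2 million draws per setting). With 50–85% of patients above the CAT cut and 40–50% above the mMRC cut:
- latent CAT–mMRC correlation 0 to 0.8: 12.5–15.4%;
- latent correlation 0.5 to 0.7: 13.0–14.7%.

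**4. Both nulls must be rejected.** A false joint claim requires rejecting at least one true null at 5%, so the error is at most 5%. With both nulls true and correlation 0.5 it is 0.05 + 0.05 − 0.091 = 0.9%.

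**5. Candidate remedies.**
- Fixed sequence, each step at 5%: if the CAT null is true, any error requires a CAT rejection. If it is false, any error requires an mMRC rejection. Either way the error is at most 5%.
- Splitting alpha, 2.5% each: 1 − 0.975² = 4.94% if independent, and never above 5%. For 0.50 against 0.60 at 385 per cohort, power falls from 79.8% to 70.9%, and 470 per cohort would be needed for 80%.

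**The case against.** **Each null names its own instrument.** If CAT and mMRC are reported as two distinct claims, each keeps its own 5%. If both are required, there is no inflation. This stands as a limit on the arithmetic: the figures in steps 2 and 3 apply only if any one rejection suffices. It does not remove the gap, because the plan adopts none of these readings.

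**The proportions may be descriptive.** They have no null, 3.4.1 only presents them, and 4.5 treats the dichotomous form as an alternative to the continuous one. This largely stands, and so the four-test figure is only conditional. Against it, 3.5 calls proportions the primary outcome measures, and 4.3 allows chi-square and similar comparisons of outcome measures.

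**The specific tests are placed elsewhere.** Section 4.1 puts them in separate table shells, and several sections refer to a separate SAP. Neither is in the text reviewed, so a rule may exist there. But 4.1 promises the tests for each objective, not a statement of which result decides.

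**The study is an observational convenience-sample survey with a largely descriptive purpose.** Strict familywise control is arguable in that setting. This bears on how serious the point is. Naming the deciding analysis in advance is worthwhile in any setting.

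Two stronger readings are tempting. A reader might infer that the proportions will be compared unweighted, because 3.4.1 does not mention weighting. Section 4.4 applies IPTW to the symptom-burden comparison in general, which plausibly covers them. A reader might also infer that the sized endpoint is simply not the tested one. Section 4.5 allows the dichotomous form to be modelled, so the form is undecided rather than plainly mismatched.

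**Conclusion.** The point holds as a missing decision rule. One primary objective has two unlinked nulls and two further primary proportions on which the study was sized, and the model outcomes and their form can be chosen after results are reviewed.

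The size depends on how the gap is filled, always at an assumed two-sided 5% per test:
- either null suffices: about 7–10%, for correlation 0.9 down to 0;
- the two proportions are formally tested as well: about 12–15%;
- both nulls required: at most 5%.

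A reader might take an inflated rate as an established property of the plan. The documents do not support that, because they state no test-level alpha, no CAT–mMRC correlation and no any-one-suffices rule. The effect of choosing outcomes after review under 4.5 is not in these figures and could add to them. The point should be settled before outcomes are seen, but it does not invalidate the design.

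**What to change.** - **3.6:** name one deciding analysis before outcomes are seen. One option is a fixed sequence: the IPTW-weighted comparison of CAT total score at two-sided 5%, then mMRC score at 5% only if CAT is significant. The protocol does not rank the instruments, so the order is the sponsor's choice; what matters is that it is fixed in advance.
- **3.4.1 and 4.3:** report the CAT ≥10 and mMRC ≥2 proportions as IPTW-weighted differences with confidence intervals, as supportive results, and reconcile the ≥10 and >10 cuts across sections.
- **3.5 and the synopsis:** stop calling the proportions the primary outcome measures, and describe 385 per cohort as a precision figure for each proportion. Either tie the 80% power statement to a stated difference or remove it.
- **4.5:** fix the outcome and its form in advance and remove their selection after review of results.

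The cost is wording in several sections, with no new data or patients. CAT keeps its full 5% and loses no power, unlike under a split alpha. The downside is that mMRC cannot be claimed alone if CAT is not significant.
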